A porcine bridging hernia repair study demonstrated that PhasixTM Mesh could perform as a durable scaffold for soft tissue repair when spanning a surgical defect. The results of the 52-week study showed that the repair site had significantly greater mechanical repair strength, as compared to native abdominal wall. This persisted even after significant PhasixTM Mesh resorption (as measured by molecular weight). PhasixTM Mesh showed an initial mild-moderate host inflammatory response, that declined to mild over 52 weeks. Neovascularization (angiogenesis) and new collagen deposition were evident at 6, 12, 26 and 52 weeks. In a 24-week rat study, histological analyses of the repair site demonstrated that some competitive meshes had a greater overall host inflammatory response, some had less of a response and one had a very similar response, to PhasixTM Mesh. In the same study, histological analyses demonstrated similar variability on measures of host fibrotic response.

MonoMax® suture (B. Braun Melsungen AG) is a product made from the same polymer as Phasix™ Mesh. A twelve month, 150-patient, multicenter clinical study demonstrated the safety and efficacy of MonoMax® for abdominal wall closure. Wound infection and wound dehiscence rates were compared between MonoMax® and an historical control (7.3% versus 11.3% combined). One year after surgery, the rate of incisional hernias was similar comparing the two groups: 21 patients (14.0%) in the MonoMax® group compared to 30 patients (21.3%) in the control.

This post-approval clinical study is being conducted to evaluate the use of PhasixTM Mesh in primary ventral, incisional or multiply-recurrent hernia repair in patients with a higher level of risk as defined by the presence of 1 or more common pre-existing conditions. Patients who receive a PhasixTM Mesh implant will be followed for 60 months.

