#### 5.2 Eligibility Criteria – Enrollment Period

#### 5.2.1 Inclusion Criteria

The subject must meet all of the criteria listed below to be enrolled in the study:

- 1. Subject must be 18 years of age or older
- 2. Subject or subject's legally authorized representative must be willing to give written informed consent
- 3. Subject must be diagnosed with primary ventral, incisional hernia or multiplyrecurrent (not to exceed 3 recurrences) ventral or incisional hernia
- 4. Subject must have a hernia greater than  $10 \text{ cm}^2$  and  $\leq 350 \text{ cm}^2$
- 5. Subject must be willing to undergo initial ventral, incisional or multiply-recurrent incisional hernia repair using retro-rectus or onlay placement (using absorbable suture) with or without Component Separation Technique (CST)
- 6. Subject is expected to meet the criteria for a Class I wound as defined by the CDC (Appendix 4)
- 7. Subjects must have 1 or more of the following pre-study conditions:
  - a. Body Mass Index (BMI) between 30-40 kg/m^2, inclusive
  - b. Active smokers (if attempts to quit smoking within two weeks of surgery have failed and the patient is still an active smoker at the time of surgery)
  - c. COPD presence on patient self-report
  - d. Diabetes mellitus
  - e. Immunosuppression
  - f. Coronary Artery Disease
  - g. Chronic corticosteroid use: greater than 6 months systemic use
  - h. Serum albumin less than 3.4 g/dL
  - i. Advanced age: 75 years or older
  - j. Renal insufficiency, defined as serum creatinine concentration  $\geq 2.5 \text{ mg/dL}$

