#### 5.2.2 Exclusion Criteria

The subject must be excluded from study enrollment if any of the following criteria are met:

- 1. Subject has had 4 or more previous hernia repairs (of the index hernia)
- 2. The subject has peritonitis
- 3. The subject is on or suspected to be placed on chemotherapy medications during any part of the study
- 4. The subject's Body Mass Index (BMI) is greater than  $40 \text{ kg/m}^2$

- 5. The subject has cirrhosis of the liver and/or ascites
- 6. Subject is American Society of Anesthesiology Class 4 or 5
- 7. Subject is known to be infected with human immunodeficiency virus (HIV)
- 8. Subject has a life expectancy of less than 2 years at the time of enrollment
- 9. Subject has any condition that, in the opinion of the Investigator, would preclude the use of the study device, or preclude the subject from completing the follow-up requirements
- 10. Subject's hernia repair utilizes intra-abdominal mesh placement
- 11. Subject has a surgical wound classified as Class II (Clean-Contaminated), Class III (Contaminated) or Class IV (Dirty-Contaminated) as defined by the CDC (Appendix 4)
- 12. Subject has an active or latent systemic infection
- 13. Subject requires surgical bridge repair as the sole repair
- 14. Subject is pregnant or has plans to become pregnant during the study period or is currently breastfeeding
- 15. Subject has enrolled in another clinical study within the last 30 days
- 16. Subject is part of the site personnel directly involved with this study
- 17. Subject has a known allergy to the test device or component materials (patients with known allergies to tetracycline hydrochloride or kanamycin sulfate should be avoided).

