#### 6.5 Withdrawal and/or Early Termination

Subjects will be informed that they have the right to withdraw from the study at any time, without affecting their future care. Subjects may also be discontinued from the study, if the Investigator determines it is in the best interest of the subject.

Additionally, subjects may be discontinued for reasons including, but not limited to the following:

- Consent is withdrawn
- Lost to follow-up (LTF)
- Death
- Investigator withdrawal of subject
- Other

A subject is considered LTF if the investigational site personnel are unable to locate the subject despite two documented attempts to notify the subject via telephone and a third attempt by certified mail.

A subject is considered an Early Termination (ET), if discontinuation occurs after successful implant of the test device. The site should attempt to bring the subject back to complete all ET visit study procedures (see Table of Study Events).

Once a subject discontinues from the study, the Investigator must complete a Study Completion eCRF and the reason for subject discontinuation must be fully documented.

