#### 7.1 **Study Hypothesis**

There is no formal statistical hypothesis for this observational post-market study. The study will follow eligible, high risk patients implanted with the PhasixTM Mesh for hernia repair in order to assess long-term recurrence and surgical site infection rates.

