# 7.2 Sample Size Considerations

This study is projected to enroll up to 120 subjects at approximately 16 sites. The sample size of 120 subjects is based on potential adequacy of data to meet the study objectives. It is not based on any statistical consideration.

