#### 4.4 Analysis of Primary and Secondary Variables

No formal hypothesis will be stated and statistically tested. All primary and secondary variables will be analyzed using descriptive methods. Any statistical testing, if performed, will be considered exploratory and will be based on a two-sided 5% significance level. No adjustment for multiple testing will be done. The primary and secondary variables will additionally be analyzed using the PP set (including the subgroup analyses by gender but no further subgroup analyses).

Changes from baseline will be calculated as follows:

Absolute change = post-baseline/ post procedure result – baseline result

In the following the details on the specification, definition, or calculation of the primary and secondary variables will be given.

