Additionally, a Kaplan-Meier analysis for time from surgery to hernia recurrence will be performed and graphically displayed. Subjects without hernia recurrence will be censored at the last date at which they were known to have no hernia recurrence (i.e. date of completion or discontinuation from the end of study page or the last visit date if the subject was lost to follow up).

The time to event (first time of hernia recurrence as defined above) will be calculated as date difference (in days) between date of surgery (Day 0) and start date of the corresponding AE when a hernia recurrence occurred first time.

Kaplan-Meier analysis (tables and curves) will also be performed for the subgroups defined in section 3.4 above. Median time will be compared between the male and female subjects using the log-rank test. If the sample size is too low to perform an adequate valid log-rank test, the test results will not be presented.

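### The Kaplan-Meier analysis of hernia recurrence censors deaths, so one minus Kaplan-Meier at 60 months modestly overstates the proportion of patients who recur

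*SAP*

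**What the plan says.** SAP 4.4.1, under hernia recurrence rate, adds a Kaplan-Meier analysis of time from surgery to first recurrence. Its censoring rule is: "Subjects without hernia recurrence will be censored at the last date at which they were known to have no hernia recurrence". The date used is the one on the end-of-study page, or the last visit for a subject lost to follow-up. Nothing separate is said about death.

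Protocol 6.5 introduces its list of reasons with "Additionally, subjects may be discontinued for reasons including, but not limited to the following", and death is on that list. The rule therefore covers deaths by implication. SSI is to be analysed in the same way.

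Three further parts of the plan bear on the point:

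- **Follow-up.** Protocol 1.1: "Patients who receive a Phasix TM Mesh implant will be followed for 60 months".
- **Eligibility.** Protocol 5.2.2 excludes a patient if "Subject has a life expectancy of less than 2 years at the time of enrollment". Protocol 5.2.1 requires at least one of ten risk conditions, of which one is "Advanced age: 75 years or older".
- **Other recurrence summaries.** SAP 4.4.1 gives rates for separate time intervals and one overall rate, each with exact 95% confidence intervals. The overall rate takes no account of how long each subject was followed.

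**The concern.** A patient who has died cannot have a recurrence later. Censoring at death treats that patient as still able to recur, at the same rate as the survivors. The resulting curve answers a hypothetical question: how many would recur if nobody died? As an estimate of the share of patients who recur, one minus Kaplan-Meier is too high whenever event-free deaths come before later recurrences. The gap grows with follow-up.

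Protocol 7.1 gives long-term recurrence as one of the two things the study is to assess, and Kaplan-Meier is the only planned summary that yields a cumulative 60-month figure while allowing for unequal follow-up. Unequal follow-up is to be expected, since the extension needs ethics approval at the site and renewed consent (Protocol 5.3 and 6.3.3.1). A reader is therefore likely to take the 60-month Kaplan-Meier value as the proportion of patients who recur.

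**Working it through.** **What there is to reproduce.** The plan states no expected recurrence rate, mortality or power. Of the sample size, Protocol 7.2 says: "It is not based on any statistical consideration". The check is therefore one of direction and size, over assumed ranges.

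**Inputs.** F is one minus Kaplan-Meier at 60 months, assumed 10% to 46%. The upper end is the background figure for large defects in Protocol 1.1. D is 60-month mortality, assumed 5% to 30%. Follow-up of 5 years and n = 120 come from the documents.

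**Formula.** With independent constant hazards, λr = −ln(1 − F)/5 and λd = −ln(1 − D)/5. The proportion who actually recur, which is the Aalen-Johansen target, is

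CIF = λr/(λr + λd) × [1 − exp(−5(λr + λd))].

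**Worked case, F = 20% and D = 10%.** 5λr = 0.2231 and 5λd = 0.1054. The ratio is 0.2231/0.3285 = 0.679. The bracket is 1 − 0.80 × 0.90 = 0.28. CIF = 0.679 × 0.28 = 19.0%, a gap of 1.0 point.

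**Range.** Each cell gives the CIF, with the gap to F in percentage points in brackets.

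| F | D = 5% | D = 10% | D = 20% | D = 30% |
|---|---|---|---|---|
| 10% | 9.8% (0.25) | 9.5% (0.50) | 9.0% (1.02) | 8.4% (1.56) |
| 20% | 19.5% (0.49) | 19.0% (0.98) | 18.0% (2.00) | 16.9% (3.07) |
| 30% | 29.3% (0.71) | 28.6% (1.44) | 27.1% (2.93) | 25.5% (4.50) |
| 46% | 45.0% (1.04) | 43.9% (2.11) | 41.7% (4.30) | 39.4% (6.60) |

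**Late deaths.** Suppose all deaths fall after year 2, so that λd′ = −ln(1 − D)/3 applies over the last three years only. Then

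CIF = 1 − exp(−2λr) + exp(−2λr) × λr/(λr + λd′) × [1 − exp(−3(λr + λd′))].

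At F = 20% the gaps become 0.28, 0.57 and 1.16 points for D = 5%, 10% and 20%. Across the table they shrink by about 40% to 45%.

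**Sampling error.** The exact 95% interval for 24/120 is 13.3% to 28.3%, a half-width of (28.3 − 13.3)/2 = 7.5 points. This is a best case, because Protocol 6.1.2 counts subjects as enrolled at consent, so fewer than 120 may be implanted.

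**Does the overall rate serve instead?** A simulation of 400,000 subjects with F = 20% and an assumed 30% loss to follow-up gave:

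| D | 1 − KM | Aalen-Johansen | Crude overall rate |
|---|---|---|---|
| 10% | 20.0% | 19.0% | 16.2% |
| 20% | 20.0% | 18.0% | 15.4% |

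The crude rate counts early leavers as event-free and is too low, by more than Kaplan-Meier is too high.

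**SSI.** Appendix 3 of the protocol limits superficial SSI to 30 days and deep SSI with an implant to one year. With SSI risks of 5% to 20% and D up to 30%, the gap is at most 0.06 points if events fall within 30 days, and at most 0.7 points if they fall within 12 months. Only if SSIs were spread evenly over 60 months would it reach 0.1 to 3.1 points.

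**The case against.** The strongest case against acting has four parts.

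- **Kaplan-Meier is supplementary.** Both documents introduce it as an addition to the rates, and neither says that one minus Kaplan-Meier will be quoted as the proportion who recur. With independent censoring it is a valid estimate of net risk. This stands as far as it goes: the plan makes no false statement. It does not remove the need for a cumulative figure, because the interval rates are not cumulative and the overall rate is biased low by early leavers.
- **No decision turns on it.** Protocol 7.1 states: "There is no formal statistical hypothesis for this observational post-market study". There is no performance threshold, and the gap lies within sampling error. This stands and keeps the point minor. The gap is nevertheless systematic and one-sided, and no confidence interval reflects it.
- **Mortality may be low.** A reader might infer from the eligibility rules that deaths are expected. The documents do not support that. One condition of ten is enough for entry, and a BMI of 30 to 40, smoking or diabetes qualifies alone. ASA class 4 or 5, cirrhosis, and current or anticipated chemotherapy are excluded, and no mortality figure is given. Permitted and plausible is as far as the text goes.
- **Deaths will already be visible.** SAP 4.1 shows status at end of study with the reason for early termination. A count of deaths is therefore not missing from the plan.

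**Conclusion.** The concern holds for hernia recurrence, as a minor reporting point. Subjects who die without recurrence are censored, no cumulative incidence estimate is planned, and one minus Kaplan-Meier at 60 months then exceeds the proportion of patients who recur. The direction is certain if any event-free deaths precede later recurrences. The size is not known from the documents: about 0.5 to 2.0 points at a 20% net risk with 5% to 20% deaths, under independent constant hazards, and a little over half of that if deaths come after year 2.

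Two wider readings are tempting and should not be drawn. One is that the SSI estimate is affected to the same degree. Under the Appendix 3 windows nearly all countable infections precede the deaths in question, and the effect is negligible. It would matter only if late infections were counted, which the SAP's SSI question, having no time limit, does not rule out. The other is that the bias distorts comparisons between age groups. SAP 3.4 plans subgroups by gender, center, pre-operative diagnosis and surgical procedure, none by age, and the documents do not show that these groups differ in mortality.

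**What to change.** In SAP 4.4.1, for hernia recurrence:

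- State that subjects who die without a recurrence are censored in the Kaplan-Meier analysis, and label that curve as net risk.
- Add the Aalen-Johansen cumulative incidence, with death from any cause as competing event and 95% confidence intervals. Quote this as the proportion of patients with recurrence.
- Take the reason and date from the end-of-study page, where SAP 5 says both are recorded.

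For SSI the same addition is optional.

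The cost is a short SAP amendment, one extra table and one extra figure. No new data are needed. The drawback is that the report must explain two curves that will differ slightly.

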# 6.3.3.1 Roll in Visit

The Roll in Visit should be completed in clinic where eligible subjects should be reconsented and confirmed that no abdominal surgeries were performed at the site of the index procedure. Sites with IRB approval of the extension study may complete the Roll in Visit with eligible subjects in combination with the 36 Month Follow Up visit.

6.3.3.2 30 Month Follow Up (910 days  $\pm$  30 days), 42 Month Follow Up (1275  $\pm$  30 days), 54 Month Follow Up (1640 days  $\pm$  30 days)

A telephone contact should be scheduled with the subject and completed by the Investigator. The following information will be collected:

- Symptoms suggestive of hernia recurrence
- Symptoms suggestive of surgical site infections
- Any adverse events relating to the device, procedure, or abdominal space since the last study assessment

If the Investigator determines the responses provided by the subject demands a physical exam be conducted, an office visit will be scheduled. The office visit will be included as part of the 30, 42 or 54 Month Follow Up assessment (not an Unscheduled Visit) and will require all study assessments listed in Section 6.3.3 to be completed.

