##### 4.4.1 Analysis of Primary Variables

###### Hernia recurrence rate

Hernia recurrence rates will be assessed by physical examination at each study visit through 60 months. A recurrent hernia will be defined as any hernia identified or confirmed by the investigator, during any study follow-up visit, in approximately the same position as the hernia repaired in the study procedure. Potential hernias identified via incidental magnetic resonance imaging (MRI) or computed tomography (CT) scan will be evaluated by the operating surgeon for clinical significance and confirmation of hernia recurrence.

Hernia recurrence (after surgery including UVs) is defined as follows:

- The question “Is there any evidence of hernia recurrence in the same location as the index procedure per physical exam?” is answered with “yes”

or

- the question “Is there any evidence of hernia recurrence in the same location as the index procedure by any other means?” is answered with “yes”.

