## 5 Changes from Protocol

In the following any changes on statistical aspects as described in the protocol are given:

- In the study protocol, chapter 7.3, it is specified that demographics and baseline characteristics will be summarized using the ITT population. In this SAP it is planned to present the in-/ exclusion criteria (with reason for failure to meet eligibility criteria) and demographics (listing only) for the ITT set. Further baseline characteristics are not foreseen to be presented as they are not postulated to be documented in the eCRF (see study protocol, chapter 6.1.3, describing screening failures: “At a minimum, subject demographics and the reason for failure must be collected; ...”).

- According to the study protocol, section 7.3, the primary endpoints of hernia recurrence rate and surgical site infections rate will be reported by visit. The calculation of rates at each time point will be based on available data at the time point. Missing data will not be imputed.

In the SAP it is planned to present the respective rates in time intervals (Post OP – 1 month/ > 1 month – 3 months/ > 3 months – 6 months/ > 6 months – 12 months/ > 12 months – 18 months/ > 18 months – 24 months/ > 24 months – 30 months/ > 30 months – 36 months/ > 36 months – 42 months/ > 42 months – 48 months/ > 48 months – 54 months/ > 54 months – 60 months). In case a scheduled visit was not performed but the subject had a visit afterwards, the total number of subjects will not be reduced for the time interval as the subject is still in study. If no information is available that the event occurred until the missed visit, no event is assumed for that time interval.

- In the study protocol in section 6.4 'Table of study events' an early termination (ET) visit is mentioned together with an unscheduled visit what implies a separate ET visit. However, no separate ET visit is realized in this study, just last sequential visit is available with documentation of reason for withdrawal and date of discontinuation on end of study (EoS) page

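### For subjects who discontinue, the Kaplan-Meier censoring date can fall after the last check for recurrence, and it differs from the date used for subjects lost to follow-up

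*SAP*

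**What the plan says.** - **Censoring rule.** SAP 4.4.1, Hernia recurrence rate: "Subjects without hernia recurrence will be censored at the last date at which they were known to have no hernia recurrence". The same sentence spells this out as the "date of completion or discontinuation from the end of study page", with the last visit used instead for subjects lost to follow-up.
- **How recurrence is found.** Same section: "Hernia recurrence rates will be assessed by physical examination at each study visit through 60 months". Evidence by other means also counts, and SAP Section 4 brings unscheduled visits into the primary endpoints.
- **Early termination.** Protocol 6.5 says "The site should attempt to bring the subject back to complete all ET visit study procedures", and the Table of Study Events lists a physical examination there. SAP Section 5 says "no separate ET visit is realized in this study, just last sequential visit is available", together with a reason and a discontinuation date on the end-of-study page.
- **Months 30, 42 and 54.** Protocol 6.3.3.2: "A telephone contact should be scheduled with the subject and completed by the Investigator". The call covers symptoms of recurrence and infection. An office visit follows only if the answers call for one.
- **Event date.** SAP 4.4.1 dates a recurrence by the start date of its adverse event. It does not say whether that means onset or detection.
- **Other uses of the date.** SAP 4.4.1 uses the same end-of-study or last-visit date for the study duration behind the interval denominators, and analyses surgical site infection in the same way.

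**The concern.** The rule states a principle and then gives a date that need not satisfy it. A discontinuation date on a form shows when participation ended, not when the repair was last checked. Protocol 6.5 lists consent withdrawal, death, investigator withdrawal and other reasons alongside loss to follow-up. All of these except loss to follow-up take the form date.

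Two consequences follow. Unassessed time can enter the risk set of a primary-endpoint analysis as recurrence-free time. And two subjects with the same last examination can be censored up to about a year apart solely because of the reason recorded for leaving. The SAP gives no ground for that difference.

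**Working it through.** There is no planned figure to reproduce. The documents give no expected recurrence or dropout rate, and Protocol 7.2 says that the 120 subjects have no statistical basis. All rates below are assumptions.

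**1. Longest gap.** After month 24 the scheduled clinic examinations are at days 730, 1095, 1460 and 1825. The nominal gap is 1460 - 1095 = 365 days. With the ±30-day windows in SAP Section 4 it is (1460 + 30) - (1095 - 30) = 425 days, and longer if a visit is missed. If telephone contacts at days 910, 1275 and 1640 count as assessments, the longest nominal gap is 1460 - 1275 = 185 days.

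**2. Two leavers compared.** Suppose that two subjects were last seen at day 1095. One withdraws consent at day 1455 and the other is lost. They are censored at days 1455 and 1095, which is 1455 - 1095 = 360 days apart on the same information.

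**3. Why it can matter.** The estimate at 60 months is 1 - ∏(1 - d/n), where d is the recurrences and n the subjects at risk at each event time. A leaver kept in n after the last assessment enlarges n without being able to add to d. This changes the estimate only if events are dated between examinations. If every event is dated to a scheduled examination, a leaver who goes between two examinations is out of n by the next one under either rule.

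**4. Size, range of rates.** Simulation of 1,000,000 subjects per scenario, with clinic examinations at days 30, 90, 180, 365, 545, 730, 1095, 1460 and 1825. Times to recurrence and to discontinuation (other than loss to follow-up) are independent and exponential, with daily hazard -ln(1 - risk)/1825. Recurrences surface only at examinations and are dated to onset.

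| 60-month recurrence / discontinuation (assumed) | End-of-study date | Last examination | Difference (points) |
|---|---|---|---|
| 10% / 10% | 9.98% | 10.06% | 0.1 |
| 20% / 20% | 19.8% | 20.1% | 0.3 |
| 30% / 40% | 29.1% | 30.1% | 1.0 |

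The mean gap was about 127 to 137 days per discontinued subject, which adds 0.8% to 3.8% unexamined person-time. When events were dated to the scheduled examination days, the difference was 0.0 in every scenario.

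**5. Size, by how recurrences surface.** Same schedule, recurrence 0.05 per year, so the true 5-year risk is 1 - exp(-0.25) = 22.1%. Withdrawal is 10% per year. The share of recurrences found between examinations is assumed.

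| Found between examinations | Dating of the rest | End-of-study date | Last examination |
|---|---|---|---|
| 0% | onset | 21.3% | 22.1% |
| 0% | detection | 22.1% | 22.1% |
| 50% | onset | 21.7% | 22.4% |
| 50% | detection | 22.1% | 22.4% |
| 100% | not applicable | 22.1% | 22.9% |

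Repeat runs moved single entries by about 0.1 point. The worst error is 21.3 - 22.1 = -0.8 points for the SAP rule and 22.9 - 22.1 = +0.8 for examination-only censoring. Censoring at the last visit with telephone contacts included ran from about -0.3 to +0.5 points, the smallest worst case of the three.

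**6. Scale.** An exact 95% interval for 24 of 120 is 13.3% to 28.3%, or 15.0 points wide.

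**The case against.** The strongest case against is that the SAP rule can be the better one. Recurrences need not wait for a scheduled examination. Any abdominal evaluation triggers an unscheduled visit with a physical examination, evidence by other means counts, adverse events are collected until participation ends, and the calls ask about symptoms. If most recurrences surface this way, a subject is in effect under observation until discontinuation, and cutting back to the last examination counts the events found between visits while deleting the event-free time. The last row of the second table shows this. The objection stands against examination-only censoring. It does not remove the mismatch between the SAP's stated principle and its date, or the different handling of subjects lost to follow-up.

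Three narrower points also stand.
- SAP Section 5 rules out a separate early-termination visit. A reader might infer that nobody is examined at discontinuation, but the text does not say so: a subject may leave at a clinic visit, and then there is no gap.
- Completers are little affected, because month 60 includes a physical examination.
- The Kaplan-Meier analysis supplements interval and overall rates with exact confidence intervals, and no hypothesis is tested. That limits the stakes, although the interval denominators use the same date.

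**Conclusion.** The rule is internally inconsistent for subjects who discontinue for reasons other than loss to follow-up, and leavers are handled in two ways. That follows from the documents alone. The size rests on assumptions: about 0 to 1 percentage point on the 60-month estimate, for 10-30% recurrence and 10-40% discontinuation, independent of each other. This is minor beside the precision of about 120 subjects.

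A reader might infer that the rule always understates recurrence, or that censoring at the last examination removes the bias at no cost. Neither is supported. The understatement arises mainly when start dates are back-dated to onset and recurrences surface at scheduled examinations. It is nil when events are dated to those examinations, and the alternative can overshoot by a similar amount. If discontinuation is itself related to recurrence, neither date corrects for it. The effect on the infection analysis was not sized.

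**What to change.** 1. In SAP 4.4.1, censor every non-completer without recurrence, whether discontinued or lost, at the last visit (scheduled or unscheduled) at which recurrence was assessed and not found. Completers can stay as they are.
2. State that a telephone contact with the recurrence symptom questions counts as such a visit, or show the result both ways.
3. Use the same date for the interval denominators and the infection analysis. State when an interval counts as completed: a leaver last seen on day 1095 has not strictly reached the end of the interval that closes on day 1125.
4. Report censoring at the end-of-study date as a sensitivity analysis.
5. State whether the adverse event start date means onset or detection.
6. Reconcile Protocol 6.4 and 6.5 with SAP Section 5 on the early-termination visit.

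The cost is a few sentences and one extra Kaplan-Meier run, with no new data collection. The estimate may become slightly less favourable, and could be slightly too high if many recurrences are found between visits. The sensitivity analysis would show by how much the choice of date matters.
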